It is a cross-sectional, population-based study. Subjects who are found to meet all the inclusion and none of the exclusion criteria will be recruited. They will complete a set of sleep-related questionnaires, undergo anthropometric measurements, home polysomnographic (PSG) monitoring, attention assessment and phenotyping of their metabolic and cardiovascular risk.

Pilot Data and Sample Size Estimation

We have previously established a school-based cohort in 2003-2005 which included children aged between 6 and 13 years to determine the prevalence of OSA. [1] We then conducted a 4-year follow-up for a subgroup of the cohort was carried out. [25] At follow-up, the subjects were aged between 10 and 17 years. A total of 243 teenagers returned for the follow-up visit. The prevalence of OSA defined by different cut-offs and the minimum sample size required to detect corresponding prevalence with various levels of precision are presented in table 1. On further analysis those who returned for the 4-year follow-up had higher baseline OSA severity compared to the rest of the cohort [OAHl: 1.0 (0.1–2.5) c.f. 0.6 (0–2.0), $p=0.007$], therefore the calculated prevalence is likely an over-estimation. Nonetheless, using the proposed sample size would provide adequate power should the genuine population prevalence is lower than the calculated one.

Table 1. Minimum sample size required to detect the prevalence of OSA defined by various cut-offs with different levels of precision.

	OAHl $\geq 5/h$	OAHl $\geq 1/h$	OAHl $\geq 1/h$ + habitual snoring (ICSD criteria)
No. of cases	34/243	120/243	31/243
Prevalence	0.140	0.494	0.128
Precision			

	Minimum sample size required		
0.01	4623	9603	4276
0.015	2055	4268	1900
0.02	1156	2401	1069
0.025	740	1536	684
0.03	514	1067	475
0.04	289	600	267
0.05	185	384	171

In the current settings with limited budget allocation, our research team is capable of recruiting 740 adolescents to detect a prevalence of 14.0% with a precision of 2.5% (i.e. 95%CI: 11.5–16.5%) for the OAH1 \geq 5/h cutoff. The sample size can also ensure a precision of <4% for the OAH1 \geq 1/h cut-off and a precision of <2.5% for the ICSD criteria. [31] The sample size would also provide >99% power to detect the differences between the estimated prevalence of OSA in adolescents and the published prevalence of OSA in primary school children [1] no matter which cut-off is being used.

Sampling Frame

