Level III sleep study will be conducted at home for every subject. A model of NOX-T3 sleep monitor will be used to record the following parameters: respiratory movements of the chest and abdomen by inductance plethysmography, oxygen saturation and derived heart rate by oximetry, respiratory airflow by pressure transducer, snoring, body movement and body position. We define an adequate overnight sleep study as one with total sleep time >6 hours.

A random sample of subjects will also be invited to undergo overnight full polysomnography (PSG) in our sleep laboratory to validate the level III study (please see below for details). In our laboratory, a model Siesta™ ProFusion III PSG monitor (Compumedics Telemed, Victoria, Australia) will be used to record the following parameters: electroencephalogram from three channels (F4/A1, C4/A1, O2/A1), bilateral electrooculogram, electromyogram of mentalis activity and bilateral anterior tibialis. Inductance plethysmography will be used to record respiratory movements of the chest and abdomen. Heart rate and electrocardiogram will be obtained from 2 chest leads. Oxygen saturation (SaO₂) will be measured by an oximeter (Ohmeda Biox 3900 Pulse Oximeter) with finger probe. Respiratory airflow pressure signals and end tidal CO₂ will be recorded simultaneously via a triple-port nasal catheter placed at the anterior nares and connected to a pressure transducer and a capnograph (BCI Capnocheck Plus)

respectively. An oronasal thermal sensor will also be used to detect absence of airflow. Snoring will be measured by a snoring microphone placed near the throat. Body position is monitored via a body position sensor.

Respiratory events including obstructive apnoeas, mixed apnoeas, central apnoeas and hypopnoeas will be scored based on the recommendations from The AASM Manual for the Scoring of Sleep and Associated Events. [39] Respiratory effort-related arousals (RERAs) will be scored when there is a fall of <50% from baseline in the amplitude of nasal pressure signal with flattening of the nasal pressure waveform, accompanied by snoring, noisy breathing, or evidence of increased effort of breathing. A respiratory event is only scored when it lasts ≥ 2 breaths irrespective of its duration. [39]

Obstructive apnoea hypopnoea index (OAH), respiratory disturbance index (RDI), oxygen desaturation index (ODI), arousal index (ArI) and respiratory arousal index (RAI) are defined according to standard recommendations. [39]

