We have carried out a pilot study to validate the proposed home sleep monitor (NOX-T3). Eleven subjects aged between 12-16 years were recruited from various sources, namely attendants to the sleep disorder clinic, healthy subjects who participated in our sleep duration and blood pressure study and relatives of patients who attend our respiratory clinic. They underwent an overnight in-laboratory polysomnography (PSG) with simultaneous NOX-T3 portable monitor recording, followed by unattended home recording with NOX-T3. The mean \pm SD OAH was 5.8 ± 6.6 events/h on PSG, 6.0 ± 6.9 events/h on in-laboratory NOX-T3 recording, and 4.3 ± 4.8 events/h on home NOX-T3 recording ($p=0.6$). The intra-class correlation between OAH obtained from in-laboratory PSG and in-laboratory NOX-T3 recording is 0.982 (95% CI: 0.937-0.995), indicating an excellent agreement. On the other hand, the intra-class correlation between OAH obtained from in-laboratory PSG and home recording with NOX-T3 is 0.656 (95% CI: 0.155-0.893), indicating a moderate reliability of the home testing. Moreover, based on a cutoff of OAH ≥ 1 or 5 events/h, the Cohen's Kappa agreement between in-laboratory PSG and home testing with NOX-T3 are both high at 0.814 (SE: 0.175).

We plan to further validate this degree of agreement (Cohen's Kappa = 0.814) of the home sleep testing by recruitment more subjects during the study period to undergo both home testing and in-laboratory PSG. A sample size of 23 will provide an 80% power with a type I error of 0.05 to validate a Cohen's Kappa of 0.814 of the home sleep testing against the null hypothesis that the Cohen's Kappa is less than 0.3, i.e. a poor agreement. In other words, we will recruit another 12 random subjects during the study period, making it a total of 23 subjects for validating the home monitor.

7-day sleep pattern monitoring

Sleep will be objectively measured using actigraphs. Actigraph is a wristwatch-like device that uses a piezo-electric beam to detect movements which are translated into digital counts accumulated across predesigned epoch intervals (for example, 1 minute) and stored in internal memory. Data can then be downloaded for further analysis.

The device will be worn on the non-dominant wrist for 7 consecutive days and nights. We will instruct the parents / caregiver to keep a sleep log on bedtimes and waking times, temporary pauses in actigraph registration (for example, while taking a bath), and significant events that

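### The 80% power and 0.05 error stated for the kappa validation describe 23 new subjects, but 11 of the 23 are the already-observed pilot and only 12 are new random participants

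*Combined protocol and SAP*

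**What the plan says.** The Sleep study section reports a completed pilot of 11 adolescents, drawn from "attendants to the sleep disorder clinic, healthy subjects who participated in our sleep duration and blood pressure study and relatives of patients" attending a respiratory clinic. Comparing unattended home recording with in-laboratory polysomnography (PSG), it gives a kappa of 0.814 (SE 0.175) at both OAHI cut-offs, ≥1/h and ≥5/h.

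That estimate then becomes the alternative for a test: "A sample size of 23 will provide an 80% power with a type I error of 0.05", set "against the null hypothesis that the Cohen's Kappa is less than 0.3". The number is met by pooling: "we will recruit another 12 random subjects during the study period, making it a total of 23 subjects for validating the home monitor".

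Neither the cut-off nor the proportion positive behind the 23 is given. The null is worded directionally, but the test is not specified. No separate analysis of the 12 is described, nor any allowance for reusing the pilot.

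The section Pilot Data and Sample Size Estimation plans the main study on 14.0% at ≥5/h and says of its pilot prevalences: "therefore the calculated prevalence is likely an over-estimation".

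**The concern.** Power and type I error are properties of data not yet seen. Here 11 of 23 results (48%) were known when the sentence was written, and those same results supplied the alternative. The stated 80% and 0.05 therefore do not describe the planned pooled set. The pilot was also a convenience group in which positives were much commoner than the study expects at ≥5/h, and the precision of kappa depends heavily on the proportion positive.

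Every participant's OSA status comes from the unattended home recording, so readers will lean on this validation. The pilot's intra-class correlation with PSG was 0.656 for home recording (lower limit 0.155), against 0.982 for simultaneous in-laboratory recording. At stake is a validation claim that looks stronger than the evidence from the 12 random participants.

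**Working it through.** **Inputs from the Sleep study section.** Pilot n = 11, kappa 0.814, SE 0.175; null 0.3; alternative 0.814; N = 23 = 11 + 12; power 0.80; alpha 0.05. **From Table 1:** proportions positive 0.140 (≥5/h) and 0.494 (≥1/h). **Assumed:** all 11 pilot pairs were used, and both methods have the same proportion positive p.

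**1. Reproducing 23.** The large-sample variance of kappa times n is V(k,p) = (1−k)[(1−k)(1−2k) + k(2−k)/(2p(1−p))], and N = [(z_α√V(0.3,p) + z_β√V(0.814,p))/(0.814−0.3)]².

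At p = 0.36: √V(0.3) = 0.985 and √V(0.814) = 0.607. Two-sided, N = [(1.960×0.985 + 0.842×0.607)/0.514]² = 22.6, that is 23. At p = 0.50 it is 21.1, that is 22. One-sided, the same formula gives 17–18. A goodness-of-fit formula gives 22–23 one-sided and 28–29 two-sided. So 23 is reproducible at about 36–50% positive, and every version assumes N subjects not yet observed. At p = 0.14 the first formula needs 41 (two-sided) or 31 (one-sided).

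**2. The pilot's case mix.** Write 2×2 tables as {both positive, discordant, discordant, both negative}. With n = 11, only {4,1,0,6}, {6,1,0,4} and their transposes give 0.814. For {4,1,0,6}, observed agreement is 10/11 = 0.909, chance agreement is (5×4 + 6×7)/121 = 0.512, and kappa = (0.909−0.512)/(1−0.512) = 0.814.

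The cut-offs are nested, and kappa is 0.814 at both. Positive recordings out of 22 number 2×4+1 = 9 or 2×6+1 = 13. If any recording lay between 1 and 5/h, the counts must be 9 at ≥5/h and 13 at ≥1/h. Then 4–5 of 11 (36–45%) were PSG-positive at ≥5/h, against 14.0% planned.

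**3. Exact rejection rates.** Cell probabilities are p²+kp(1−p), p(1−p)(1−k) twice, and (1−p)²+kp(1−p). The test is z = (k̂−0.3)/√(V(0.3,p̂)/n), rejecting above 1.960 (two-sided value, upper tail only) or 1.645 (one-sided value). An undefined kappa counts as no rejection.

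| Set tested | True kappa in new subjects | 14% positive (≥5/h) | 49.4% positive (≥1/h) |
|---|---|---|---|
| 12 new alone | 0.814 | 26% / 30% | 31% / 66% |
| 23 fresh | 0.814 | 49% / 53% | 81% / 92% |
| Pilot + 12 new | 0.3 | 26% / 53% | 14–15% / 33% |
| 23 fresh | 0.3 | 2.0% / 2.8% | 1.6% / 4.9% |

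Entries are two-sided / one-sided critical value. The pooled row is conditional on the observed pilot, using {4,1,0,6} at ≥5/h and either table at ≥1/h. By this test the pilot alone gives z = 1.76, already above the one-sided value.

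**4. What the 12 can show at ≥5/h.** Expected PSG-positives are 12×0.14 = 1.7, and the chance of none is 0.86¹² = 16%. With true kappa 0.814, kappa is undefined with probability 12%. The large-sample SE at n = 12 is 0.246 at 14% and 0.168 at 49.4%, so the 95% half-widths are 1.96×0.246 = 0.48 and 1.96×0.168 = 0.33. If the true prevalence were 10% (assumed), 1.2 positives would be expected and the power of the 12 would fall to 18% / 20%.

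**The case against.** The strongest reply is that pooling pilot and new data to estimate agreement is legitimate, that the plan discloses where the pilot came from, and that it already calls home reliability only moderate. That stands, and a descriptive pooled kappa can stay. It does not rescue the sentence, which states a hypothesis test with error rates.

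Four stronger readings are tempting and are not supported:

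- *The type I error is inflated to 26% or 53%.* Those rates are conditional on a favourable pilot and combine it with a kappa of 0.3 in the new subjects. They measure the pilot's leverage, not the type I error of the stated test.
- *The pooled rate at ≥5/h could be 52% / 76%.* This needs {6,1,0,4} at ≥5/h, possible only if none of the 22 recordings lay between 1 and 5/h. In Table 1, 120−34 = 86 of 243 adolescents (35%) lie in that band. It is a limiting case.
- *The plan contradicts itself on random sampling.* The Sleep study section's earlier remark on a random sample concerns participants invited to PSG and points forward to the details. Nothing says that all 23 are random.
- *Sidedness is wholly missing.* The null is directional, which suggests a one-sided test. What is missing is an explicit test, and the formulas reach 23 under either reading.

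It also stands that no pass criterion is given and no prevalence analysis depends on this kappa.

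**Conclusion.** The concern holds as a minor point. The sample-size arithmetic is not wrong, but the stated power and error belong to a design of 23 fresh subjects at roughly the pilot's case mix, and the plan supplies 12. Independent evidence at ≥5/h carries about 26–30% power rather than 80%, and at ≥1/h about 31–66%, depending on the critical value. With the case mix planned for ≥5/h, 23 fresh subjects would not reach 80% either.

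These figures assume a null-variance z test, equal proportions positive for the two methods, all 11 pilot pairs used, and the prevalences in Table 1. The documents do not fix the test or the cut-off. The main conclusion does not depend on those choices: for either cut-off and either critical value, the 12 alone fall short of 80%.

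A reader might infer that the prevalence results are undermined. The documents do not support that: nothing makes them conditional on this test, and no prevalence estimate changes. Only the stated power and the strength of the validation claim are affected.

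**What to change.** Withdraw the 80%/0.05 sentence, or restate it for the subjects still to be observed. If a power figure is kept, name the OAHI cut-off, the sidedness and the assumed proportion positive. Suggested text:

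*Agreement between home recording and PSG will be reported in the 12 randomly selected participants separately from the 11 pilot subjects: kappa at OAHI ≥1/h and at ≥5/h, and the mean home-minus-PSG difference in OAHI, each with a 95% CI. Any pooled kappa is descriptive. At ≥5/h about 1.7 PSG-positive participants are expected among the 12, or fewer if 14.0% is an over-estimate.*

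The cost is protocol wording and one split table, with no extra recordings or PSG nights. The downside is a less favourable stated power and visibly wide intervals for the 12. Keeping a genuine 80% claim would instead need about 23 new subjects at 36–50% positive, 11 more than planned, and more at 14%.

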(3) There is accumulating evidence of 2 types of childhood OSA, namely one associated with lymphoid enlargement in the absence of obesity, and the other being primarily associated with obesity. [10] This classification of childhood OSA allows better distinction between patients. Evidence also suggests that genetic susceptibility of OSA has both obesity-dependent and obesity-independent components, thus emphasizing the importance of segregating obese and non-obese subjects in OSA research. [11] The OSA subtypes are distinct entities. Former is the classical childhood OSA and the latter being more akin to adulthood OSA where obesity plays an important role. As obesity is becoming more common among adolescents, [12] we can expect to see an increasing prevalence of OSA in this age group. Furthermore, research in this area may provide the important answer as to whether adulthood OSA begins from adolescence.

Relevance, significance and value of the study

With the obesity epidemic, the prevalence of OSA in adolescents will be expected to increase further. Taking into account the association between OSA and clinically important short and long term complications, our proposed study is highly relevant and will yield vital information on disease burden. Our study will also form a platform from which repeated measurements can be made to assess time trends and to answer the important question of whether adulthood OSA takes its origin from adolescence. This study, with both significant academic and clinical value will invariably enrich the scanty scientific literature on adolescent OSA. It will also build on our internationally recognised track record on OSA research.

(a) Background of research

Why study OSA?

The prevalence of childhood OSA is quoted to be around 1 to 5%. [13] However in studies that utilized parental report with additional diagnostic testing, the prevalence is as high as 12-24%. [13] The variation in reported prevalence can be explained by the use of different methodologies and diagnostic cut-offs. In Hong Kong, our research group has completed an OSA prevalence study in community-based children aged 5 to 13 years. We used a two-phase strategy, namely questionnaire screening followed by overnight sleep study and we found a prevalence rate of 3-

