5% using ICSD-II diagnostic criteria. [1] Obstructive sleep apnoea in adolescents is largely unexplored, and the only publication on its prevalence has quite a few methodological flaws, namely small sample size and failure to represent the general population. [5]

It is well documented that childhood / adolescent OSA can lead to a variety of important sequelae which include cardiovascular, growth, neurocognitive and behavioural deficits together with metabolic disturbances. [6-9] Individuals with OSA have higher morbidity, mostly related to respiratory diseases and health care use starting from a young age. [14] They are also found to have poorer quality of life scores than healthy controls. [15] Therefore this proposal deals with an important condition that is currently insufficiently researched.

Two types of childhood OSA

Recent research has emphasized the “newer” type of childhood OSA, namely primarily obese subjects with only mildly enlarged lymphoid tissue. These obese children with OSA present differently and have distinct clinical phenotypic characteristics from non-obese children with OSA. [10] Different metabolic and immunological changes are present in obese children with OSA, and obesity can induce health changes that are independent from an isolated upper airway problem. Therefore the distinction between obese children with OSA from those of normal weight is very crucial. This newer type of childhood OSA is more akin to adulthood OSA as obesity is the major component in both. There is accumulating evidence that this type of childhood OSA begins in adolescence. [16]

Obstructive sleep apnoea in childhood usually remit by adolescence, and a large proportion of adolescents OSA cases are incident cases. Distinct risk factors for OSA are at play at each time point across paediatric ages, underscore the need to separate OSA research for children and adolescents. [16,17]

Why study adolescents?

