The resultant prevalence will be compared to published prevalence of OSA in children. Logistic regression analysis will be used to identify possible risk factors of OSA in adolescents. Potential factors associated with a higher risk of OSA may include male sex, body weight, waist circumference, neck circumference, tonsil size, modified Mallampati score and chronotype. All these factors will be first assessed in univariate analysis. Those found to be significantly associated with OSA in univariate analysis will be assessed in multivariate model. The association between OSA and cardiovascular, metabolic and cognitive outcomes will be investigated. Comparisons will be made between subjects with and without OSA. Linear regression analysis will be conducted to assess the association between these outcomes and OAH. Multiple linear regression analysis will be performed to see if OAH is independently associated with these outcome measures while adjusting for possible confounders such as body mass index. The significant level will be set as $p < 0.05$. All analyses will be performed using SPSS version 20.0.

Feasibility and Timetable of Project

The proposed study will require a total of 30 months (130 weeks) to complete. We will be able to assess 8 subjects per week. For a sample size of 740, we will need 93 weeks for data collection. The first 12 weeks will be used for document preparation and school recruitment. The last 15 weeks will be used for data cleaning and analysis. The remaining 10 weeks should be allowed for clashes with schooling, missed appointments and public holidays.

Education plan

The principal investigator and the collaborator are all experienced teachers and supervisors. This project can further strengthen the educational activities and exchanges of the respective departments. It will also provide a good opportunity to train undergraduate and postgraduate students, especially for someone who is interested in the field of sleep medicine. The student will be provided with the required theoretical and practical training, and will work under close supervision of the principal investigator and related research personnel. This will allow the student to learn the knowledge and skills as a scientist, an ideal opportunity to advance himself / herself.

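### The planned comparison with the published child rate cannot show a difference between adolescents and children as such, because case finding, definition and period also differ

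*Combined protocol and SAP*

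**What the plan says.** The Hypothesis section states a single hypothesis: adolescent prevalence differs from the reported child figure. Statistical Analysis deals with it in one sentence: "The resultant prevalence will be compared to published prevalence of OSA in children". It names no test, reference value, case definition or adjustment. The covariate adjustment described later in that section belongs to the regressions of cardiovascular, metabolic and cognitive outcomes on OAHI.

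Pilot Data and Sample Size Estimation identifies the comparator as the group's own published study of primary school children, and states: "The sample size would also provide >99% power to detect the differences between the estimated prevalence of OSA in adolescents and the published prevalence", "no matter which cut-off is being used".

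That child study is described in two places. Pilot Data: "We have previously established a school-based cohort in 2003-2005". Background of research: "We used a two-phase strategy, namely questionnaire screening followed by overnight sleep study", giving a rate of 3 to "5% using ICSD-II diagnostic criteria". Key Issues (1) gives 5.8% for boys and 3.8% for girls.

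For the adolescents, Sleep study provides a home Level III recording for every subject. Outcome Measures defines the primary outcome by OAHI without a cut-off. Sampling Frame uses 2016 by-census figures, so recruitment is in 2016 or later.

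On why published child rates vary, Background of research says: "The variation in reported prevalence can be explained by the use of different methodologies and diagnostic cut-offs".

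**The concern.** The two rates differ in three respects besides age.

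- **Case finding:** screening and then a sleep study in the children; a sleep study for everyone in the adolescents.
- **Definition:** ICSD-II for the child rate; OAHI with no cut-off for the adolescents. The ICSD form in Table 1 also requires habitual snoring.
- **Period:** 2003-2005 against 2016 or later, at least 11 years apart. Key Issues (3) and the section on relevance both expect adolescent OSA to rise with obesity.

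The protocol accepts that methods and cut-offs move reported prevalence, yet plans nothing to deal with either in its own comparison. A gap produced by procedure or period would be reported as a difference between adolescents and children, and the high stated power would make it look conclusive. Biases in opposite directions could equally hide a real difference.

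**Working it through.** **1. The plan's own figures.** Sample size is 1.96² × p(1 − p)/d². With p = 34/243 and d = 0.025 this gives 739.7, so 740 reproduces. Half-widths at 740 are 3.6 points for OAHI ≥ 1/h and 2.4 points for ICSD, matching the plan.

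For power I used a one-sample, two-sided 5% test against a fixed child rate p0, with n = 740 (the plan does not state sidedness). Take p1 = 31/243 = 0.1276 (ICSD, Table 1) and p0 = 0.05, the top of the 3-5% range:

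- null SE = √(0.05 × 0.95/740) = 0.00801
- alternative SE = √(0.1276 × 0.8724/740) = 0.01226
- z = (0.1276 − 0.05 − 1.96 × 0.00801)/0.01226 = 5.04, so power exceeds 99.9%

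The stated power reproduces for ICSD, and lower values of p0 only raise it. The documents give no child rate at OAHI ≥ 1/h or ≥ 5/h, so the claim for those cut-offs cannot be checked like for like.

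**2. What a non-age gap would do.** Suppose there is no age effect and procedure or period alone multiplies the rate by f, so p1 = f × p0. Then

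P(significant) = Φ[(p1 − p0 − 1.96·s0)/s1] + Φ[(p0 − p1 − 1.96·s0)/s1],

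where s0 = √(p0(1 − p0)/740 + se²), s1 = √(p1(1 − p1)/740 + se²), and se is the standard error of the published child rate. The documents give neither f nor se; both are assumptions.

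Worked case, p0 = 4%, f = 1.5, p1 = 6%:

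- se = 0: s0 = 0.00720, s1 = 0.00873, first term Φ(0.67), probability 75%
- se = 1.0 point: s0 = 0.01232, s1 = 0.01327, first term Φ(−0.31), probability 38%

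| Assumed gap f | Assumed se (points) | p0 = 3% | p0 = 4% | p0 = 5% |
|---|---|---|---|---|
| 1.25 | 0 | 25% | 30% | 36% |
| 1.5 | 0 | 64% | 75% | 83% |
| 1.5 | 0.5 | 47% | 61% | 72% |
| 1.5 | 1.0 | 26% | 38% | 50% |
| 2.0 | 0 | 98% | >99% | >99% |

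These figures assume independent subjects. With an assumed design effect of 2 for schools and se = 0, the 1.5-fold row becomes 41, 50 and 58%.

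For scale: if screening were the only difference and screen-negative children were counted as non-cases (an assumption), f = 1.5 means that screening missed one third of cases.

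**3. Direction.** Missed screen-negatives would lower the child rate. The documents do not say how screen-negatives entered it; if it was corrected for them, this part shrinks. Two features could lower the adolescent rate. In the device pilot (n = 11), mean OAHI was 4.3 at home against 5.8 on laboratory PSG (p = 0.6, so weak evidence). The exclusion criteria also remove adolescents with past upper airway surgery or current OSA treatment. The net sign cannot be determined from the documents.

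**The case against.** The strongest reply is that the plan never claims an age effect. The hypothesis refers to the reported child figure, and the power sentence to the published prevalence; both can be addressed as written. That stands: the limit is on interpretation. It is still worth fixing, because the rationale of the study is that adolescents are distinct from children, and a significant result would naturally be read that way.

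A second reply is that the comparison is not a listed outcome, that the sample size rests on precision, and that the primary estimate is untouched. That also stands, and it limits how serious the point is.

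Several stronger readings are tempting but not supported:

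- *The power claim is wrong.* It reproduces for ICSD.
- *The plan uses this test to prove that child rates cannot be extrapolated.* Key Issues (1) and the section on why adolescents are studied argue that from developmental change, as a premise stated before any data.
- *Screening is shown to have depressed the child rate.* The higher published range does not show this: "However in studies that utilized parental report with additional diagnostic testing, the prevalence is as high as 12-24" (per cent) describes parental report plus testing, not testing everyone. The ratio of 12% to 5% is therefore no measure of screening bias.
- *The plan will set adolescent OAHI ≥ 1/h against a child ICSD-II rate.* Table 1 has 120 cases against 31, so that mismatch would decide the result, but no section proposes it. The power sentence may assume matching child rates from the cited study, which would settle the definition issue but not case finding or period.

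**Conclusion.** The point holds as a limit on interpretation, and the change is worth making. As written, the comparison can establish that the adolescent rate differs from a published number. It cannot attribute that difference to adolescents and children as such, because case finding, definition and period differ at the same time and nothing in the plan separates them.

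The size of the bias is unknown and its direction is not fixed. The 1.5-fold illustration (64, 75, 83% with the child rate fixed; 26, 38, 50% with an assumed standard error of 1.0 point) shows only that a moderate non-age gap could plausibly produce significance. It rests on an assumed gap, no age effect, independence and child rates of 3, 4 and 5%. It is not an estimate of what will happen, and a reader should not infer that the bias must be upward. The primary prevalence estimate is unaffected.

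**What to change.** 1. In Statistical Analysis, name the comparator and use the same definition in both groups for this comparison: ICSD, the only one with a child rate in the documents, or an OAHI cut-off re-estimated from the group's own child data.
2. Add a secondary like-for-like analysis. Apply the child study's screening rule to the adolescents' questionnaire answers and compare that two-phase-equivalent rate with the child rate. Keep the all-tested rate as the primary prevalence. If the instrument cannot be used at ages 12-16, give a sensitivity range for screening sensitivity and home-device bias. State how screen-negative children entered the published rate.
3. Report the difference with a 95% confidence interval that carries the child study's standard error, standardised for sex and BMI z-score if the child data allow. State that it cannot be attributed to age alone, because method and period differ. The period difference remains even after item 2.
4. In Pilot Data and Sample Size Estimation, limit the power sentence to the definition or definitions for which a child rate is given.

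Cost: at most one added questionnaire per participant (none if the sleep habit questionnaire in the Abstract is the same instrument), some re-analysis of the group's child data, and a weaker conclusion on adolescents against children. The questionnaire must be in place before data collection. No extra sleep studies are needed, and sample size and the primary estimate do not change.
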